### 3. ABBREVIATIONS

AE	Adverse event
ANOVA	Analysis of variance
AUC	Area under the curve
CHO	Carbohydrate
CPET	Cardiopulmonary exercise test
CRF	Clinical records file
ECG	Electrocardiogram
EDTA	Ethylenediaminetetraacetic acid
eHSP	Extracellular heat shock protein
GCP	Good clinical practise
GH	Growth hormone (human)
Hb	Haemoglobin
HbA1 c	Haemoglobin adult type 1 c (Glycated haemoglobin)
Hct	Haematocrit
HEC	Hyperinsulinaemic-euglycaemic clamp
HIIT	High intensity interval training
HR	Heart rate
HRV	Heart rate variability
HSP	Heat shock protein
IL	Interleukin
LF	Low frequency
NHS	National Health Service
NIHR	National institute for health research
NIRS	Near infrared spectroscopy
NRES	National research ethics service
OGTT	Oral glucose tolerance test
PCPI	Patient, carer and public involvement
PPI	Patient public involvement
QUICKI	Quantitative insulin sensitivity check index

REC	Research ethics committee
RHR	Resting heart rate
RMR	Resting metabolic rate
RMSSD	Root mean square of the successive differences
RSA	Respiratory sinus arrhythmia
SAE	Serious adverse event
T2DM	Type 2 diabetes mellitus
T rec	Rectal temperature
UoP	University of Portsmouth
VO 2	Oxygen consumption
WHO	World health organisation

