**Participants and Recruitment:** A power calculation indicates (looking for a difference in paired means) that 15 people are required to detect a 1 standard deviation change in insulin sensitivity ( $\alpha = 0.05$ ; power = 80%). Given the magnitude of change shown in other chronic passive heating studies [60] it is not unreasonable to expect to see this effect size (see 10.1). To account for participant drop-out we intend to recruit 20 people aged  $> 35$  years with T2DM (as defined by the World Health Organisation (WHO), with an HbA1c  $> 48$  (mmol/mol). Participants will be excluded from the study if they have uncontrolled hypertension (systolic blood pressure  $> 180$  mmHg); a history of myocardial infarction or cerebrovascular events; leg ulcers; unable to give informed consent or any other serious medical condition which would interfere with safety or data interpretation.

Participants will be recruited from a database of known individuals with T2DM who attend outpatient clinics at the Queen Alexandra Hospital (Portsmouth) and via posters and word of mouth within the University of Portsmouth. We will also recruit from local GP practices via mail outs.

**Consent and Screening:** Visit 1 will act as a screening, consent and familiarisation ( $\sim 1$  h). Participants will be given the opportunity to ask any questions they may have after reading the participant information sheet. A standard medical history and clinical examination will be undertaken by a member of UoP staff, including for example height, mass, electrocardiogram, ankle-brachial pressure index and blood sample collection for lipids and biochemical markers, and liver function tests. Seated resting blood pressure measurements will be performed to calculate systolic, diastolic blood pressure.

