#### 10.3 Screening and Enrolment

**Consent and Screening:** Visit 1 will act as a screening, consent and baseline assessment (~1 h). Participants will be given the opportunity to ask any questions they may have after reading the PIS. A standard medical history and clinical examination will be undertaken by a member of UoP staff, including height, mass, electrocardiogram, full blood count and HbA1c. Seated resting blood pressure measurements will be performed to calculate systolic, diastolic blood pressure.

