### **Secondary Outcomes:**

#### *Biomarkers*

Blood samples will be taken at screening in EDTA tubes for assessment of full blood count and HbA1c. Fasting and area under the curve (AUC) plasma [glucose] will be assessed as a marker of glucose control. Change in circulating plasma [Growth Hormone (GH)] (EDTA, K2, BD, NJ, USA) will be assessed due to its diabetogenic effects via gluconeogenesis and glycogenolysis from the liver and kidneys and suppression of glucose uptake in adipose tissue [59, 60]. Change in circulating plasma [Butyrate] (EDTA K2, BD, NJ, USA) caused from alterations in gut microbiome [64] will be assessed due to its effect on insulin secretion [65],

insulin action [65] and inflammatory status [66]. Change in circulating plasma [eHSP70] (EDTA K2, BD, NJ, USA) will be assessed due to eHSP's role in reducing inflammatory status. Change in circulating plasma [IL-6] (EDTA K2, BD, NJ, USA) and [IL-10] (LH, BD, NJ, USA) will be assessed to determine inflammatory status. Blood samples for assessment of fasting plasma [glucose], HbA1c, [GH], [Butyrate], [eHSP70], [IL-6] and [IL-10] will be from the venous collection at a fasted state and at the end of the 120 min OGTT for AUC plasma [glucose] and insulin sensitivity only. With exception to screening samples which will be taken for analysis immediately after visit, all samples will be immediately placed in a chilled (4°C) centrifuge and spun at 4000g for 10 min. Once spun, the plasma will be pipetted into Eppendorf's and placed into a -80°C freezer for storage. Additional biomarkers may be looked at in future if extra funds become available.

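### Section 10.6 takes HbA1c from the fasted draw, but its handling rule spins every non-screening sample and stores only plasma, in which HbA1c cannot be measured

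*Combined protocol and SAP*

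**What the plan says.** Section 7.2 lists HbA1c as the fourth of 19 secondary outcomes, and section 3 expands the term as "Glycated haemoglobin".

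The Biomarkers paragraph of section 10.6 deals with HbA1c twice. It first provides an EDTA sample at screening for full blood count and HbA1c. It then places HbA1c in the fasted collection together with plasma analytes: "Blood samples for assessment of fasting plasma [glucose], HbA1c, [GH], [Butyrate], [eHSP70], [IL-6] and [IL-10] will be from the venous collection".

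The handling rule follows directly. Its only exception is "With exception to screening samples which will be taken for analysis immediately after visit". For everything else, "all samples will be immediately placed in a chilled (4°C) centrifuge and spun at 4000g for 10 min". The next sentence begins "Once spun, the plasma will be pipetted into" and ends with storage at -80 °C. Section 10.1 names where screening blood is analysed and does not mention any other blood.

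On the baseline, section 10.3 says "Visit 1 will act as a screening, consent and baseline assessment", with an examination "including height, mass, electrocardiogram, full blood count and HbA1c", and section 13.1 describes the visit in the same way. Section 7.1 instead says "Visit 1 will act as a screening, consent and familiarisation".

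**The concern.** The protocol plans an assay that needs red cells, and then applies to the same blood a rule that keeps the plasma. Screening samples, which include an HbA1c sample, are exempt from the rule; the exemption does not extend to the experimental visits.

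What is at stake is one declared secondary outcome. Section 14.2 compares pre with post by a paired samples t-test or Wilcoxon signed-rank test, so each participant needs both values. Frozen plasma could not supply a missing HbA1c later. The rule is the same for every participant and visit, so following it to the letter would affect the whole sample and would not produce scattered missing values.

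**Working it through.** The protocol states no figure that needs reproducing here. The check is a comparison of sections, followed by simple counts.

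**Step 1: is HbA1c meant to be measured at the experimental visits?** Yes. It is a secondary outcome (7.2), outcomes are assessed less than 72 h before and less than 72 h after the intervention (10.6), and the fasted draw lists it by name.

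**Step 2: what happens to that blood?**

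| Visit | HbA1c sample drawn? | Handling in the text | Form provided for |
|---|---|---|---|
| Screening | Yes, EDTA | Exempt from the spin; analysed straight after the visit | Suitable |
| Pre | Yes, tube type not given | Spun at once; plasma frozen | Plasma only |
| Post | Yes, tube type not given | Spun at once; plasma frozen | Plasma only |

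**Step 3: can plasma yield the outcome?** No. By the protocol's own expansion the analyte is a form of haemoglobin, and haemoglobin is in the red cells.

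**Step 4: does another section give a route?** I found none. No section keeps an unspun tube or the cell fraction from an experimental visit, and none sends non-screening blood to a laboratory for HbA1c.

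**Step 5: which value is the baseline?** The sections conflict.
- For the screening value: 10.3 and 13.1 call Visit 1 a baseline assessment, and the Biomarkers paragraph, under the Secondary Outcomes heading, opens with the screening sample.
- For the pre-visit value: 7.1 describes the pre and post visits as identical, the Figure 1 note refers baseline blood to 10.6, and 10.6 sets the 72 h window.
- The interval from screening to the pre visit is not stated, so nothing ties the screening value to that window.

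**Step 6: size.**
- Share of secondary outcomes: 1/19 = 5.3%.
- Post-visit samples under the rule: 1 × 15 = 15 at the required sample size and 1 × 20 = 20 if all recruits complete (section 9).
- Pre and post samples together: 2 × 15 = 30 to 2 × 20 = 40.

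**The case against.** The strongest reply is that this is a slip in one general sentence. Nearly all the surrounding analytes are plasma analytes, and the rule goes straight on to pipetting plasma. The same paragraph sends screening HbA1c directly for analysis, so the team evidently knows that it needs a different route, and staff may well keep a whole-blood tube in practice. Much of this stands. It is why the point is an inconsistency to correct and not a deliberate design choice. It does not remove the point: a rule that covers all samples with one named exception tells staff to spin the HbA1c tube.

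A reader might infer more, in three ways.
- That no HbA1c sample is taken at the experimental visits. Section 10.6 does provide for the draw; the handling is what fails.
- That every HbA1c pair, 15 to 20 of them, is certain to be lost. That only multiplies the literal reading by the sample size. The text does not say that the packed cells are thrown away.
- That the pre-intervention value is necessarily missing too. If the screening result is the intended baseline, a suitable pre value exists. The documents leave this open.

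It can also be said that HbA1c will move little. Section 4 calls a fall over 3 weeks surprising, given haemoglobin turnover of about 115 days, and this intervention runs within 14 days. That limits what the outcome can show, and makes a modest gap between screening and the pre visit less important. It does not explain listing an outcome whose sample is handled in a way that cannot produce it.

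**Conclusion.** The point holds as a minor internal inconsistency. Followed literally, section 10.6 turns the post-visit HbA1c sample, and the pre-visit one, into plasma that cannot give secondary outcome 4, and the paired comparison would have no post value. The loss is a risk of following the rule and not a certainty.

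The effect is confined to one of 19 secondary outcomes. Insulin sensitivity and the glucose outcomes are measured in plasma and are unaffected, and the sample size does not change.

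The conclusion rests on two things: the general fact that haemoglobin is carried in red cells, and the absence from the document of any separate handling instruction for HbA1c at these visits. A laboratory manual outside the document could already cover it; the protocol text would still need to agree.

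Which visit supplies the baseline is a separate conflict. The post-visit problem is the same under either answer.

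**What to change.** 1. In section 10.6, widen the exception to the spin rule so that it covers screening samples and one EDTA whole-blood tube for HbA1c at each experimental visit, sent unspun for analysis. The rest of the handling rule and the outcome list can stay.
2. In section 10.1, extend the named laboratory route for screening blood to these tubes.
3. Separately, reconcile sections 7.1, 10.3, 10.6 and 13.1 and state which HbA1c value is the baseline. The pre-visit value is the one that meets the 72 h window in section 10.6. If the authors intend the screening value, they should say so and give the permitted interval before the intervention.

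The cost is a few sentences and the transport of an unspun tube after each experimental visit, at most 2 × 20 = 40 tubes. Some visits may fall at a weekend, since section 16.1 offers weekend testing, so the route must work then too. The HbA1c assays are not an added cost, because section 10.6 already plans them from the fasted draw.

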#### 10.5 Study intervention

*Daily passive heating:* Participants will attend the laboratory on 8-12 occasions within a period of 14 days (~ 90 min per visit) with the aim of completing 10, at any point in the day. Anyone completing less than 8 will be excluded from analysis. During each visit participants will self-insert a rectal thermistor and will then be immersed into a hot tub (~ 40 °C) for 60 min. Body position will be manipulated as required to achieve and maintain a target  $T_{rec}$  at 38.5 °C using 40 °C water. Aural temperature will also be measured every 15 min for determination of

validity and time lag compared to  $T_{rec}$ , for possible use in future studies. BP will also be measured at 15 min intervals after passive heating in the first intervention visit to firstly, establish safety data on the protocol (i.e. to avoid syncope) and secondly, be used as a benchmark for recovery time in subsequent intervention visits. Participants will be required to wear a bathing suit and a t-shirt for all heating visits.

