## 10.6 Study Assessments

Study assessments of the outcome measures will take place before ( $< 72$  h) and after ( $< 72$  h) the intervention. The pre- and post- experimental visits should take  $\sim 3$  hours. Briefly, in line with OGTT guidelines, participants will arrive at  $\sim 0800$  following an overnight fast. The research coordinator will confirm with the participants that they have completed a 48 h food and physical activity log, that no exercise has been performed and that no alcohol or caffeine has been consumed on the day before. To ensure that participants arrive in a euhydrated state, they will be asked to consume  $\geq 17$  mL·kg $^{-1}$  of water before each visit. Participants will rest for 15 min in a semi-recumbent position, in comfortable ambient conditions (23 °C, 50% relative humidity), then have baseline bloods (collected via venipuncture), ECG, central haemodynamics, RMR collected / measured and brachial artery FMD measurements will start followed by iontophoresis. At  $\sim 0830$  a 2 h OGTT will start with the ingestion of a glucose drink (Rapilose, 75 g glucose). At the end of the OGTT after bloods have been taken again, participants will be provided with a snack. A detailed description of the outcome measures are given below.

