### **14.2 Analysis of Endpoints**

All data will be tested for normality. Where data are not normally distributed, a nonparametric test will be performed. Data will be presented as means  $\pm$  SD. Statistical analyses will be performed on SPSS software version 24.0 (Chicago, IL). Statistical difference will be accepted when  $P < 0.05$ . Statistical differences will be assessed by paired samples t-test or Wilcoxon signed –rank test (for non-parametric data).

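### No haemoglobin or haematocrit is taken at the pre and post visits, so changes in five plasma biomarkers could be confounded by a change in plasma volume that the plan cannot measure

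*Combined protocol and SAP*

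**What the plan says.** Section 7.2 lists plasma eHSP70, IL-6, IL-10, butyrate and growth hormone among 19 secondary outcomes.

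Section 10.6 (Biomarkers) covers the blood handling:
- At screening: "Blood samples will be taken at screening in EDTA tubes for assessment of full blood count and HbA1c". Sections 7.1, 8.2 and 10.3 also place the full blood count at screening, and nowhere else.
- At the experimental visits: "Blood samples for assessment of fasting plasma [glucose], HbA1c, [GH], [Butyrate], [eHSP70], [IL-6] and [IL-10] will be from the venous collection" in the fasted state. Hb and Hct are not on that list.
- After the draw, with screening blood excepted: "all samples will be immediately placed in a chilled (4°C) centrifuge and spun at 4000g for 10 min". Then: "Once spun, the plasma will be pipetted into Eppendorf's and placed into a -80°C freezer for storage".

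Section 10.6 (opening paragraph) sets the conditions before the draw. On fluid: "To ensure that participants arrive in a euhydrated state, they will be asked to consume" at least 17 mL per kg of water before each visit. On posture: "Participants will rest for 15 min in a semi-recumbent position". Arrival is at about 0800 after an overnight fast, in a room at 23 °C and 50% humidity.

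Between the two draws, section 10.5 says "Participants will attend the laboratory on 8-12 occasions within a period of 14 days", each with 60 min in water at about 40 °C. On the analysis, section 14.2 says "Statistical differences will be assessed by paired samples t-test", or by the Wilcoxon test. Plasma volume is not mentioned anywhere in the text.

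**The concern.** A plasma concentration is an amount divided by a volume. If plasma volume differs between the two draws, the concentration moves even when the circulating amount has not. The exposure is a repeated heat load, and the post draw comes less than 72 h after it ends, so a shift in plasma volume is plausible, although the documents neither state nor size one. Water intake has no upper limit, no time window and no check, so it may also differ between a participant's two visits.

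What is at stake is interpretation. Section 10.6 reads IL-6 and IL-10 as inflammatory status, and butyrate, growth hormone and eHSP70 as mechanism. Expansion pushes all five concentrations down: it could imitate a fall in IL-6 and hide a rise in eHSP70, IL-10 or butyrate. Without Hb and Hct at both visits, nobody can check afterwards whether this happened.

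**Working it through.** **Inputs from the protocol.** 15 evaluable pairs and a two-tailed 5% level (section 9); P < 0.05 with paired tests (section 14.2); 20 recruited (section 9).

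**Inputs not in the protocol, so assumed.** Plasma-volume rise (dPV) of 3%, 5%, 10% or 15%. SD of the within-person change in the log concentration of 0.15, 0.30 or 0.50. Circulating content unchanged between draws. The plan gives no figure of its own to reproduce.

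**Step 1: dilution.** Measured concentration = content-matched concentration / (1 + dPV). For a 10% rise, 1/1.10 = 0.909, a fall of 9.1%.

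**Step 2: chance of P < 0.05 from dilution alone.** Standardised effect d = ln(1 + dPV)/SD; power of the two-sided paired t-test from the noncentral t distribution with 14 degrees of freedom and noncentrality d × √15. Example: dPV 10%, SD 0.15 gives ln(1.10) = 0.0953, d = 0.0953/0.15 = 0.635, noncentrality 0.635 × 3.873 = 2.46, power 63%.

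| Assumed plasma-volume rise | Change in concentration | SD 0.15 | SD 0.30 | SD 0.50 |
|---|---|---|---|---|
| 3% | -2.9% | 11% | 6.5% | 5.5% |
| 5% | -4.8% | 22% | 9% | 6.4% |
| 10% | -9.1% | 63% | 21% | 10.6% |
| 15% | -13.0% | 92% | 39% | 17% |

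The last three columns are for 15 pairs. With all 20 participants evaluable and a 10% rise, they become 77%, 27% and 13%. The calculation is on the log scale and the plan tests raw values, so the figures are indicative.

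**Step 3: masking.** By the same arithmetic, a true 10% rise in content with a 10% rise in volume gives 1.10/1.10 = 1.00, so no change is seen.

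**Step 4: would Hb and Hct recover the shift?** The Dill-Costill formula is dPV = (Hb pre/Hb post) × (1 − Hct post)/(1 − Hct pre) − 1. Take an illustrative baseline of Hb 140 g/L and Hct 0.42, that is 42 parts red cells and 58 parts plasma. A 10% rise makes plasma 63.8 and the total 105.8. Then Hb post = 140 × 100/105.8 = 132.3, Hct post = 42/105.8 = 0.397, and (140/132.3) × (0.603/0.58) − 1 = 0.10. With red-cell volume fixed, the shift is recovered. Both readings need whole blood from both visits; frozen plasma gives neither.

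**Step 5: is whole blood available?** The sample-handling text describes storing plasma only. Yet the same section lists HbA1c from the same fasted draw, and HbA1c is a red-cell measure that stored plasma cannot supply. Either some whole blood is kept and the text omits it, or HbA1c cannot be measured as written. The passage needs amending either way.

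**The case against.** The strongest reply is that the premise comes from outside the documents: no passage gives a plasma-volume change, and the 3-15% range has no anchor in the text. This stands, and it is why the point is put as possible confounding of unknown size.

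Second, fixed content is a strong assumption over two weeks. Markers that are continuously produced and cleared may return to their usual concentration despite a larger volume. This stands too. It means a corrected value is not automatically the better one.

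Third, the endpoints are defined as plasma concentrations. A fall in concentration is then a real fall in the endpoint; only its mechanistic reading is open. This stands, so the measured values should remain the endpoints.

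Fourth, the visits are already standardised for posture, fasting, time of day, room conditions and prior exercise. These controls limit acute shifts on the day. They neither measure nor correct a change sustained over the intervention period, and the water rule sets no common volume or timing.

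A reader might go further in four ways that the documents do not support:
- That a control arm would solve the problem. Expansion caused by heating would not occur in unheated participants, so a comparison with them would not remove it.
- That a change which vanishes on correction is not due to heating. Expansion caused by heating is itself an effect of heating.
- That correction is ruled out because all blood becomes plasma. The HbA1c listing implies whole blood from the same draw; what is missing is the Hb and Hct reading, and centrifuging is not the fault.
- That Hct in the abbreviation list shows a dropped measurement. The list also holds CPET, NIRS and QUICKI, for which no procedure is described, so it proves nothing.

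**Conclusion.** The gap is real but modest. As written, the plan has no Hb or Hct at either experimental visit and no plasma-volume step in the analysis. A change in the five markers therefore cannot be separated into dilution and altered amount, at the time or later.

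How much this matters depends on two quantities that the documents do not give. For a marker with low within-person variation (SD 0.15), dilution alone could reach P < 0.05 with a chance of 11-92% over the assumed range. For a variable marker (SD 0.50) the chance is 5.5-17%, which at the lower end is hardly above the nominal 5%. All of these figures assume fixed content. A reader might infer that plasma expansion will produce false biomarker changes; the documents do not establish that it occurs, or that it would usually reach significance if it did.

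Only mechanistic secondary outcomes are in question here. The point is worth acting on because the remedy is cheap and the chance to apply it is lost once the samples are spun.

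**What to change.** **Section 10.6.** Measure Hb and Hct on the fasted EDTA whole blood before spinning, at both experimental visits. Calculate and report the percentage plasma-volume change. State how whole blood is kept for HbA1c. Ask each participant to repeat at the post visit the water volume and timing used at the pre visit, and record both.

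**Section 14.2.** Keep the measured concentrations as the endpoints. Add plasma-volume-corrected values (post value × (1 + dPV)) for eHSP70, IL-6, IL-10, butyrate and growth hormone as a sensitivity analysis, and state that the correction assumes fixed circulating content. Where measured and corrected results disagree, do not interpret the change as altered production or release of the marker, or as altered inflammatory status.

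**Cost.** At most 20 × 2 = 40 routine Hb/Hct readings on blood drawn at visits already planned, one derived variable, and a second version of five secondary results to report. No visit is added and the intervention does not change.
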